3.3.2 Total Number of Study Sites/Total Number of Subjects Projected

The study will be conducted at 16 investigative sites in the United States.

Recruitment will stop when 500 subjects are enrolled with samples collected. It is expected that up to 550 subjects will be recruited to produce 500 evaluable subjects for the plasma biomarker aims, and approximately 475 evaluable subjects for the mRNA aims to account for subjects with only partial samples collected.

3.4 Study Population

3.4.1 Inclusion Criteria

- 1) acute (≤ 7 days of risk factor) respiratory failure requiring invasive mechanical ventilation
- 2) age > 44 weeks corrected gestational age and < 17.5 years
- 3) invasive mechanical ventilation via endotracheal tube
- 4) bilateral infiltrates on chest radiograph
- 5) oxygenation index (OI) ≥ 4 ; or oxygen saturation index (OSI) ≥ 5 on 2 consecutive measurements at least 4 hours apart but < 24 hours apart
- 6) invasively ventilated ≤ 7 days before meeting above radiographic and oxygenation criteria

3.4.2 Exclusion Criteria

- 1) weight < 3 kilograms
 - 2) cyanotic congenital heart disease (other than Patent Foramen Ovale (PFO) or Patent Ductus Arteriosus (PDA))
 - 3) tracheostomy at time of screening
-

-
- 4) invasively ventilated for > 7 days when meet ARDS criteria above
 - 5) cardiac failure as predominant cause of respiratory failure
 - 6) primary obstructive airway disease (asthma, bronchiolitis) by judgement of clinician as the primary cause of respiratory failure
 - 7) alternative known chronic lung disease as cause of respiratory failure (cystic fibrosis, eosinophilic pneumonia, interstitial pneumonitis, pulmonary hemosiderosis, cryptogenic organizing pneumonia)
 - 8) severe neurologic morbidity not expected to survive > 72 hours
 - 9) any limitations of care at time of screening
 - 10) previous enrollment in this study

Subjects that do not meet all of the enrollment criteria may not be enrolled. Any violations of these criteria must be reported in accordance with IRB Policies and Procedures. We limited enrollment to subjects < 17.5 years to preclude any subjects from turning 18 during their PICU stay (median length of ventilation for ARDS in 9 days).

4 STUDY PROCEDURES

4.1 Screening Visit

Subjects will be screened daily at the respective PICUs by trained research coordinators. Intubated subjects will be assessed for study eligibility by chart review, and if necessary, discussion with the treating team. No subjects or parents/guardians will be approached for consent until deemed eligible. Potential subjects will not be asked screening questions prior to obtaining informed consent.

All individuals meeting all inclusion criteria and none of the exclusion criteria will be approached for study enrollment within 24 hours of meeting eligibility criteria. After confirming eligibility, patients will be approached for informed consent

4.2 Study Period

4.2.1 Enrollment window

Study procedures will be performed at enrollment for all subjects. Subjects will be eligible ≤ 24 hours after eligibility, defined as the time-point of the second qualifying OI or OSI (see Inclusion criteria). Study procedures are:

- Start of paper CRF and uploading into web-based Redcap database
- Blood collection for plasma and mRNA analysis

4.2.2 Discharge

Subjects will be followed for duration of PICU stay until PICU discharge, death, or 90 days after enrollment. Data for the stay will be collected in the paper CRF and uploaded on-site to a web-based Redcap database.

4.3 Subject Completion/Withdrawal

Subjects may withdraw from the study at any time without prejudice to their care. It will be documented whether or not each subject completes the clinical study.

5 STUDY EVALUATIONS AND MEASUREMENTS

5.1 Screening and Monitoring Evaluations and Measurements

5.1.1 Medical Record Review

All clinical data will be generated at the discretion of the care team and attending physician. The following data will be abstracted from the medical chart (paper or electronic):

Category	Data to be Collected
Demographic	Date of birth, date of PICU admission/transfer, date of discharge, gender, race/ethnicity, weight, height
Medical history	Comorbid illnesses, lung injury diagnosis, organ failure score
Blood gas data	PaO ₂ , PaCO ₂ , pH
Ventilator data	Mode of ventilation, peak inflating pressure, mean airway pressure, positive end-expiratory pressure, compliance, dead space fraction
Laboratory data	White blood cell count, chemistries, lactate
Outcomes	Ventilator days, PICU survival
Vital Status	Alive or deceased at PICU discharge

5.1.2 Laboratory Evaluations

Example: Blood sampling will be performed for the following laboratory evaluations

- Plasma biomarker measurements
- Genome-wide mRNA expression from whole blood

5.1.2.1 Blood Sampling

A total of 6.1 mL whole blood will be taken from each patient within 24 hours of meeting study eligibility.

5.1.2.2 Blood Processing

Whole blood will be collected in 3 tubes. Two sodium citrate (“light blue top”) tubes will receive 1.8 mL each (total = 3.6 mL). These two tubes will be centrifuged within 30 minutes (2000 g for 20 minutes at 20°C). Plasma samples (supernatant) will be divided into aliquots and stored at -20°C at sites other than CHOP, and then sent to CHOP every 2 weeks on dry ice, where they will be stored long-term at -80°C.

An additional 2.5 mL will be stored in a PAXgene tube for RNA, stored upright at room temperature for 4 to 24 hours, and then stored at -20°C at sites other than CHOP, and then sent to CHOP every 2 weeks on dry ice, where they will be stored

long-term at -30°C. Analyses will be conducted on both plasma and mRNA at CHOP, using enzyme-linked immunosorbent assays (ELISAs) or the Molecular Biology Core for microarray, as appropriate.

5.2 Safety Evaluation

Patient safety will be monitored by noting any adverse events that occur during or as a consequence of study blood collection. Study blood collection should pose no increased risk for complications greater than that of standard clinical blood collection, and total blood volume collected does not exceed age/weight-appropriate maximums (which is why < 3 kg weight is an exclusion criteria).

6 STATISTICAL CONSIDERATIONS

6.1 Primary Endpoint

The primary endpoint of Aim 1 is successful performance of the PARDSEVERE risk stratification tool to discriminate 28-day mortality in pediatric ARDS. The primary endpoint of Aim 2 is application of a known 100-gene classifier to test whether transcriptomic endotypes exist in pediatric ARDS. The endpoint of Aim 3 is generation of novel proteomic and transcriptomic endotypes.

6.2 Secondary Endpoints

Secondary endpoints will include association of endotypes with mortality and ventilator-free days at 28 days.

6.3 Control of Bias and Confounding

While not completely possible to control for bias in an observational study, we have taken certain steps to minimize the risk of confounding. The primary exposure is biomarker (protein or mRNA)-defined endotypes. Clinical data will be collected on paper CRFs on-site and uploaded to a central, web-based Redcap server. Biomarker measurements will be made in bulk post-clinical data collection. Thus, clinical data is being collected blinded to the biomarker levels or endotype assignments. Finally, the statisticians involved in this data analysis will be blinded to outcomes (mortality); endotype assignments will be performed on presenting clinical variables and biomarker measurements.

6.4 Statistical Methods

6.4.1 Baseline Data

Baseline and demographic characteristics will be summarized by standard descriptive summaries (e.g., means and standard deviations or medians with interquartile ranges for continuous variables and proportions for categorical variables). Comparisons between survivors and non-survivors, and later between different endotypes, will be tested using unpaired t-test or Wilcoxon rank sum test for continuous variables. The analogues of these tests for > 2 groups (ANOVA and Kruskal-Wallis) will be used if > 2 endotypes are identified. Fisher's exact or chi-squared test will be used for categorical variables.

6.4.2 Analysis of Primary Outcome of Interest

For Aim 1, PARDSEVERE biomarker levels will be used to classify subjects according to the previously published PARDSEVERE decision rules without modifications [45]. This allows for assignment of 28-day mortality risk based on allocation of study subjects to one of 5 terminal nodes. Performance of PARDSEVERE will be assessed by AUROC for discriminating 28-day mortality and other diagnostic accuracy measures, including sensitivity, specificity, and positive and negative predictive values at different probability cutoffs. PARDSEVERE will

be considered validated if sensitivity is ≥ 0.85 and specificity is ≥ 0.65 , both with 95% CI width ≤ 0.16 .

For Aim 2, we will perform mRNA gene expression, and identify endotypes using a previously published 100-gene classifier [42, 43].

For Aim 3, we will identify *de novo* endotypes using LCA including biomarker and clinical variables, or novel endotypes using the entire gene expression pattern.

For the transcriptomic part of Aims 2 and 3, the cohort will be split 60:40 into a derivation and test set. In Aim 2, we will determine genome-wide differential gene expression. After filtering and normalizing, gene expression values will be ranked by median absolute deviation across all patient samples. We will then perform unsupervised agglomerative hierarchical clustering on the top 5000 probesets, with clusters allowed $k = 2-12$, as has been done to discover mRNA-based endotypes in adult sepsis [50]. To estimate k (number of endotypes), we will combine cumulative distribution functions and cophenetic distance correlation analysis to assess clustering stability. Using a random forest classifier (supervised classification with high dimensional data methods)[50, 51], we will assess ARDS endotype classification with ten-fold cross-validation of stepwise increments in gene numbers. We will decide on the final number of endotype-defining genes when the process yields a cross-validation misclassification error rate of $< 10\%$.

For the protein biomarker part of Aim 3, the cohort will be split 60:40 into a derivation and test set. We will use all measured plasma biomarkers and select clinical variables recorded within 24 hours of ARDS onset, including age, vasopressor-inotrope score [52], specific laboratory values including PELOD 2, bicarbonate, and OI at ARDS onset. These variables were chosen based on their ability to discriminate mortality in previous studies of adult [37] or pediatric ARDS [35], including by our group [34], and their ready availability within the first 24 hours of ARDS. All analyses will be performed blinded to outcome. As scales of variables vary considerably, continuous variables will be standardized to mean = 0 and standard deviation = 1 prior to analysis. We will consider models between 2 and 5 subclasses, as has been done for adult ARDS [37-39]. For LCA, criteria for model selection will be based on the Bayesian Information Criteria, the Vuong-Lo-Mendell-Rubin likelihood ratio test, and size of the smallest class. Model estimation will be based on full-information maximum likelihood methods. To avoid local maximum likelihood solutions, we will use 100 random starting values, of which the best 20 will be optimized.

For secondary aims, assuming a mortality rate of 16%, a 50:50 split between endotypes, and $\alpha = 0.05$, with 475 subjects we have 80% power to detect an association with an odds ratio ≥ 2.0 between endotype and 28-day mortality. Importantly, as the goal of endotype discovery is not mortality prediction [53], we are not powering for this outcome. Rather, we provide this calculation here for reference of what effect size endotype has on mortality that we will be able to observe.

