2.1 Primary Objective (or Aim)

This protocol has 3 specific Aims:

Aim 1: Validate and refine PARDSEVERE, a published protein biomarker-based pediatric ARDS risk stratification tool

Aim 2: Stratify pediatric ARDS into endotypes using a known 100-gene expression-based classifier to group subjects according to shared underlying biology

Aim 3: Identify *de novo* endotypes in pediatric ARDS using biomarkers and whole genome transcriptomics of peripheral blood

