3 INVESTIGATIONAL PLAN

3.1 General Schema of Study Design

The proposal is a prospective observational cohort study of pediatric ARDS taking place at 16 centers in the United States. The study involves simultaneous collection of plasma (for measurement of circulating biomarkers) and RNA-stabilized whole blood (for microarrays) within 24 hours of ARDS onset in upwards of 500 children (Figure 2).

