6.5 Sample Size and Power

For Aim 1, assuming a mortality rate of 16% and a PARDSEVERE sensitivity of 0.85 and specificity of 0.65, the sample size needed for two-sided 95% CI width of ≤ 0.16 (i.e., sensitivity of 0.85 with 95% CI 0.77 to 0.93) is 454 subjects. In our single-center study of 152 subjects and 16% mortality [45], our sensitivity was 0.96 and specificity was 0.66, suggesting that these assumptions are realistic. We have increased this to 500 total subjects with samples collected to account for ~10% of subjects being unevaluable due to sample loss or degradation during transport and storage.

For the transcriptomic Aims 2 and 3, we anticipate 475 evaluable subjects with sufficient RNA from the total cohort of 500 subjects with samples collected, assuming a conservative estimate of 5% drop-out due to neutropenia. As we found evidence for ARDS endotypes in our preliminary cohort of 67 subjects, we anticipate adequate numbers for endotype discovery. As a comparison, in adult sepsis, 4 endotypes were discovered using whole blood gene expression from 306 subjects [50].

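### The de novo whole-blood clustering has no check for leukocyte mix, so the plan cannot tell a cluster that largely reflects neutrophil share from one that reflects within-cell biology

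*Combined protocol and SAP*

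**What the plan says.** Section 3.1 plans collection of "RNA-stabilized whole blood (for microarrays) within 24 hours of ARDS onset", and section 5.1.2 lists "Genome-wide mRNA expression from whole blood". Section 5.1.2.2 confirms a PAXgene tube and describes no cell sorting.

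Section 6.4.2 sets out the de novo route. The step begins "After filtering and normalizing", without saying how. Then "gene expression values will be ranked by median absolute deviation across all patient samples", followed by "unsupervised agglomerative hierarchical clustering on the top 5000 probesets", with 2 to 12 clusters allowed. The number of clusters is chosen from cumulative distribution functions and cophenetic correlation. The number of genes is chosen from a random forest with cross-validated misclassification below 10%.

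The laboratory row of the abstraction table in section 5.1.1 reads "White blood cell count, chemistries, lactate". Section 6.3, on bias and confounding, deals with blinding. Section 2.1 says that Aim 2 is to "group subjects according to shared underlying biology". Section 6.5 sets the number evaluable for transcriptomics by "assuming a conservative estimate of 5% drop-out due to neutropenia".

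**The concern.** Whole blood is a mixture. When the neutrophil share rises in one child and falls in another, all genes expressed mainly in neutrophils, or mainly in other leukocytes, move together even if no cell has changed its behaviour. Ranking genes by variability across patients favours such genes.

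The planned quality criteria do not guard against this. Stability measures ask whether a partition is reproducible, and classification error asks whether it can be recovered from fewer genes. A partition by cell mix can do well on both.

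Interpretation is at stake. The endotypes are meant to support predictive enrichment, and section 2.2 plans to relate them to mortality, ventilation and response to therapies such as corticosteroids. If an endotype is largely a stand-in for neutrophil percentage, a routine blood count with differential already gives most of the information, and its associations would be credited to a new transcriptomic class.

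**Working it through.** **The plan's own figures.** Section 6.5: 500 × (1 − 0.05) = 475 evaluable, which reproduces. The 60:40 split in section 6.4.2 gives 0.6 × 475 = 285 for derivation and 0.4 × 475 = 190 for test. No sample-size figure changes.

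**What the documents contain on cell mix.** The sample is unsorted (3.1, 5.1.2, 5.1.2.2). One leukocyte item is listed (5.1.1). Normalization is unspecified (6.4.2). No section mentions deconvolution, adjustment for cell proportions, or a comparison of endotypes by cell proportions.

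**Simulation.** The documents give no distribution of neutrophil share and no effect sizes, so all the following inputs except the 285 subjects, the MAD ranking and the 5000 genes are assumptions: 10,000 genes; neutrophil share p with mean 0.63 and SD 0.15; log fold difference d between neutrophils and other cells, SD 1 across genes; noise SD 0.25; Ward linkage. For each child and gene:

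expression = log[p·exp(d/2) + (1 − p)·exp(−d/2)] + signal + noise

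The signal is zero, or a gene-specific shift in a random 40% of children, unrelated to p. Genes are ranked by median absolute deviation and the top 5000 clustered. AUC is that of two-cluster membership against p.

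| True signal | AUC at k = 2 | Share of variance of p explained at k = 4 |
|---|---|---|
| None | 1.00 (clusters differ by 25 percentage points in p) | – |
| Weak | 0.98 | – |
| Moderate | 0.53 to 0.56 | about 61% |

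To tie these labels to explicit signals, I ran five replicates per setting. A shift of SD 0.5 in 10% of genes gave AUC 0.98. Shifts of SD 0.5 in 40% of genes, or SD 1 in 20%, gave 0.52 with the true groups fully recovered at k = 2, and four clusters then explained 61% to 63% of the variance of p. The change-over is sharp. With SD 0.5 in 20% of genes, one set of five runs averaged 0.80 (lowest 0.52) and another averaged 0.52. With no endotype but three other continuous expression factors, the AUC averaged 0.70.

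**Other assumptions, no true endotype.** With 12,000 genes, 10% or 30% of them cell-type-specific (log2 fold SD 2), noise SD 0.3, and SD of neutrophil share from 0.08 to 0.22:
- Two clusters explained 57% to 67% of the variance of neutrophil share and differed by 0.13 to 0.37 in its mean.
- Cell-type genes made up 16% to 21% of the top 5000 when they were 10% of all genes, and 46% to 60% when they were 30%.
- With neutrophil share held essentially constant, the variance explained was about 0.

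**Do the planned criteria catch it?** In null runs with 285 derivation and 190 test subjects, ten-fold cross-validated misclassification was 4% to 10% and met the plan's limit in 7 of 8 settings. A nearest-centroid classifier stood in for the random forest. In the 190 held-out subjects the assigned groups again separated neutrophil share (AUC 0.99 or more). A composition-only partition can thus pass the error criterion and replicate in the test set.

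**The case against.** The strongest reply is that a no-endotype simulation leaves cell mix as the only structure, so any clustering must find it. Section 6.5 reports evidence of endotypes in a preliminary cohort of 67, so the null is not the plan's own scenario. This stands. A reader might infer that real signal would dilute the composition effect but never remove it. At k = 2 that is false, because a moderate signal removes it almost completely. What remains is that composition reappears at k = 4, within the plan's range of 2 to 12, and dominates at k = 2 when signal is weak.

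A reader might also infer that a differential will not be collected. The documents do not establish that. The table in section 5.1.1 is a summary by category: it also omits therapies, which section 3.3.1 says are collected, and the vasopressor-inotrope score, which section 6.4.2 uses. Cell fractions can be estimated from the arrays themselves, and section 8.1 commits to depositing the expression data, so the check would remain possible. It is still not planned.

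The 5% loss to neutropenia shows that usable RNA depends on leukocytes. It does not show that cell mix dominates variation among the 475 analysed, since it removes one extreme.

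Section 6.4.1 compares baseline characteristics between endotypes, so a gross difference in white cell count could be seen. That does not cover proportions.

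Finally, cell mix can be part of the host response, and section 1.2 describes endotypes by shared pathophysiologic, biomarker or transcriptomic profiles. A composition-related cluster may meet that definition. This stands, and it is why the adjusted analysis should not act as a gate. Following a published adult sepsis method is reasonable, but does not rule out composition effects in this cohort.

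**Conclusion.** The concern holds for the de novo transcriptomic clustering: as written, the plan cannot distinguish a cluster driven by leukocyte mix from one driven by within-cell biology. Its size cannot be fixed from the documents. Under the assumed inputs it runs from near-complete tracking of neutrophil share to almost none at k = 2, according to true signal strength, with substantial tracking at k = 4 even under moderate signal.

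The documents do not support the stronger reading that the endotypes will be artefacts of cell mix. Nor does the variability-ranking argument reach the published 100-gene classifier in Aim 2, whose genes are not selected by variability in this cohort. The clustering text in section 6.4.2 is introduced under Aim 2, but describes de novo discovery. The remedy is therefore an added sensitivity analysis with reporting, and the primary method need not change.

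**What to change.** In section 5.1.1, add the leukocyte differential from the clinical blood count nearest the study draw, with its time.

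In section 6.4.2:
1. Keep the planned clustering as primary.
2. Report cell proportions by endotype, and how well the differential alone predicts endotype assignment.
3. As a sensitivity analysis, repeat the clustering on expression adjusted for cell proportions, using the chart differential or expression-based deconvolution where it is absent. Report agreement between the two assignments.
4. Where an endotype does not persist after adjustment, state that it is largely explained by leukocyte composition, without automatically denying it endotype status.

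The cost is one more laboratory item from a chart already being abstracted and one rerun of the clustering, with no change in sample size or blood volume. Some children will have no same-day differential. Adjustment may also remove real host response expressed through cell mix, which is why it sits beside the planned analysis.

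### Section 6.4.2 does not confine transcriptomic endotype derivation to the 60% set and defines no test-set assessment, so the 40% test set is not assured to be independent

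*Combined protocol and SAP*

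**What the plan says.** Section 6.4.2 opens the transcriptomic plan with a split: "For the transcriptomic part of Aims 2 and 3, the cohort will be split 60:40 into a derivation and test set". After filtering and normalizing, "gene expression values will be ranked by median absolute deviation across all patient samples". The next step follows directly: "We will then perform unsupervised agglomerative hierarchical clustering on the top 5000 probesets", with 2 to 12 clusters allowed. The number of endotypes is chosen from clustering-stability measures. A random forest is then built, and "we will assess ARDS endotype classification with ten-fold cross-validation of stepwise increments in gene numbers".

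None of the steps after the ranking names the samples on which it is run. The one numeric criterion is this: "We will decide on the final number of endotype-defining genes when the process yields a cross-validation misclassification error rate of" less than 10%. After the sentence that creates it, the transcriptomic test set is not mentioned again.

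On numbers, section 6.5 says "we anticipate 475 evaluable subjects with sufficient RNA from the total cohort of 500 subjects with samples collected", and on that basis considers the cohort adequate for endotype discovery. Section 6.1 states what the work is for: "The endpoint of Aim 3 is generation of novel proteomic and transcriptomic endotypes".

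**The concern.** A held-out set tests whether endotypes recur only if it played no part in defining them. Here one step is described on all samples, and the clustering that follows carries no restriction. An analyst could cluster all 475 samples, train the classifier on the labels of the 60%, score it against the labels of the 40%, and still comply with the text. The test labels would then come from the same clustering as the training labels. Good agreement would show that a classifier can relearn a shared partition, not that the partition reappears in other patients.

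The cross-validation rule does not fill this gap. It measures how well a classifier recovers labels already assigned, wherever it is run. A cut through a continuous gradient can be recovered well and still not be a discrete endotype.

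At stake is the only within-study confirmation of the new transcriptomic endotypes. Section 1.2 says it is unknown whether clinically relevant endotypes exist in pediatric ARDS, so discrete structure cannot be assumed. Once test samples have entered the clustering and been seen, their independence cannot be recovered in this cohort. The blinding to mortality in section 6.3 does not help, because this dependence runs through expression data and not through outcome.

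**Working it through.** **Sizes.** Section 6.5 assumes 500 subjects and 5% loss: 500 × (1 − 0.05) = 475, which reproduces the stated figure. The split gives 0.60 × 475 = 285 derivation and 0.40 × 475 = 190 test subjects.

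**Which population does the text imply?** Section 6.5 argues adequacy for discovery from 475 and compares it with 306 subjects in an adult sepsis study. If discovery used only the derivation set, the relevant number would be 285, which is below 306. This leans towards whole-cohort discovery but does not settle it.

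**Does it matter?** The plan states no test-set agreement, so there is no figure to reproduce. Simulation was used instead, with 475 subjects split 285/190. Agreement is given by the adjusted Rand index (0 = chance, 1 = identical).

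*Run A: no discrete classes.* Gaussian data with continuous factors only; 6000 probes, top 1500 by median absolute deviation; Ward clustering cut at 2; ridge classifier in place of the random forest; 40 replicates per setting.

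| Factors | Ranked and clustered on all 475: test error (adjusted Rand) | Derived on 285, compared with independent clustering of 190: disagreement (adjusted Rand) |
|---|---|---|
| 1 | 10% (0.64) | 22% (0.36) |
| 3 | 15% (0.49) | 36% (0.10) |
| 8 | 19% (0.38) | 40% (0.05) |

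A separate repeat with the same numbers of factors gave 5%, 11% and 16% pooled, against 20%, 33% and 40%. In that repeat the pooled cross-validated error met the 10% rule in 100%, 36% and 4% of runs, although no discrete classes existed.

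*Run B: other structures.* Nearest-centroid classifier, Ward clustering, 10 to 20 replicates per setting. Entries are adjusted Rand in the test set.

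| Structure | All steps on derivation set | Ranking only on all samples | Ranking and clustering on all samples |
|---|---|---|---|
| Pure noise, 2 clusters | 0.00 | 0.00 | 0.19 (74% raw agreement) |
| Pure noise, 4 clusters | 0.00 | 0.00 | 0.14 |
| Dominated by continuous factors | 0.04–0.17 | 0.05–0.19 | 0.49–0.53 |
| Well-separated classes, 2 clusters | 0.994 | 0.993 | 0.995 |
| Well-separated classes, 4 clusters | 0.974 | 0.974 | 0.983 |

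**Ranking alone.** The probeset lists ranked on all 475 and on the 285 overlapped by about 93–94%. In pure noise with 2 clusters, the paired difference in adjusted Rand was 0.001 (standard error 0.007). A further check with 3 factors gave 0.146 and 0.160 under the two rankings.

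**Reading.** Inflation needs two things together: pooled clustering or labelling, and weak or continuous structure.

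**The case against.** The strongest reply is that everything after the split describes the derivation pipeline, so that all samples means all samples in the set being analysed. The text allows this, and nothing in it says outright that clustering is pooled. A reader might infer that the plan contradicts itself, or that the test set is in fact compromised. The documents support neither; they leave the matter open.

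Four further objections have weight.

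- **Ranking.** The one step explicitly described on all samples uses neither labels nor outcome, and its simulated effect was close to nil. A reader might take the quoted phrase itself as the source of bias. It is not; pooled clustering would be.
- **Cross-validation.** It may look incompatible with a held-out set. It is not: run inside the derivation set to choose the number of genes, it is ordinary tuning, and that is the use section 6.4.2 gives it.
- **Overstatement.** No test-set agreement measure is planned, so no planned figure is biased, and one cannot say that agreement will be overstated. The gap is that the assessment is undefined.
- **Size.** From Run A one might conclude that pooling roughly halves the error. The two columns measure different things: the second also carries the instability of a separate clustering of 190 subjects. Run A also assumes no true classes and fixes 2 clusters, where the plan allows 2 to 12.

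Aim 2's use of the published 100-gene classifier is also largely outside the point, because its gene list does not come from this clustering. The planned stability measures help to choose the number of clusters, but they do not stand in for new patients.

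What remains is that two analysts could follow the text, one pooling and one not, and only one would have a real test set.

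**Conclusion.** The point holds in a conditional form. Section 6.4.2 creates a test set of about 190 of 475 subjects, describes one later step on all samples, leaves the population unnamed for clustering, number of endotypes and random forest, and defines no test-set procedure or metric. Independent confirmation is therefore not assured.

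If clustering is also pooled, agreement can be overstated when expression structure is weak or continuous: adjusted Rand 0.19 instead of 0.00 in pure noise with 2 clusters, and about 0.5 instead of 0.04–0.17 in factor-dominated data. With well-separated classes the harm is negligible (0.98–1.00 pooled, against 0.97–1.00 without pooling). These figures rest on Gaussian data, Ward linkage and simpler classifiers than a random forest. They show direction and mechanism and do not forecast this study's result.

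The clarification should be made before the expression data are analysed. Confidence is medium, because the intended population is not stated.

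**What to change.** In section 6.4.2:

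1. Limit the ranking to derivation-set samples.
2. State that filtering, normalization parameters, probeset list, clustering, number of endotypes, gene list, cross-validation and random forest are all fixed on the 60% derivation set before the test data are opened, and that test samples are normalized with derivation-set parameters.
3. Define the test-set step: apply the locked classifier to the 40%, cluster those samples independently with the same pipeline, and report agreement between the two (misclassification, and adjusted Rand or kappa) with 95% confidence intervals. Other validation designs are possible; what matters is that one is specified in advance.
4. Keep the 10% cross-validation rule for choosing the number of genes only, and base any claim of replication on the test-set result.

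The cost is a few sentences and one extra clustering run, with no new subjects, samples or assays. The downside is that discovery rests on about 285 rather than 475 samples, so the adequacy argument in section 6.5 should be restated for 285. Reported agreement may also be less favourable.
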